4.5.6 HRCT and Surgical Lung Biopsy

4.5.6.1 High-Resolution Computed Tomography

HRCT scans should be obtained before the Screening period as part of the routine practice for a patient. It may be used to confirm eligibility. For eligibility confirmation acceptable HRCT scans should be dated not earlier than 2 years before the Screening.

Baseline HRCT scans will be performed only in those patients who have no acceptable scans within 2 months before the start of treatment period (Day 1) and had no IPF exacerbations within this period. Semiquantitative analysis of CT scans with HRCT fibrosis score calculation should be performed in each timepoint as outlined in the schedule of study assessments (see [Appendix 1](#)).

All HRCT images are to be read by the site's local radiologist reader at first. Additionally, for eligibility confirmation the HRCT scans will be reviewed by two central readers who are radiologists with expertise in IPF. If the first expert (central reader-1) agrees with the local opinion, the second expert (central reader-2) will not review scans. If the first expert disagrees with the local opinion, the second expert should review scans.

HRCT acquisition in the study will be performed using the same scanning protocol. Images in a particular site should be read by the same local specialist. Further semiquantitative assessments of CT scans for fibrosis scores will be performed by one central reader. Detailed HRCT acquisition protocol and fibrosis scoring system are described in [Appendix 2](#).

Pirfenidone—F. Hoffmann-La Roche Ltd

All HRCT digital scans should be stored on a dedicated disk or tape at each study center. The images will be transferred electronically to the central readers responsible for interpretation of the images.

Data regarding the HRCT interpretation will be entered electronically into the vendor's database and incorporated into the clinical database.

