6.4.3 Exploratory Efficacy Endpoints

HRCT fibrosis score

The HRCT findings will be evaluated using HRCT scoring system. One ILD radiologist will make assessments of 4 main findings in three zones of each lung. The six zone scores will be averaged to determine the total score for each patient. Score will be recorded at the initial diagnosis and after six and 12 months in a similar manner for further comparison. The mean \pm SD of HRCT fibrosis score like continuous variable will be determined obligatory at baseline, 6 *months* and optional at 12 months.

The values of HRCT fibrosis score at baseline, at Week 26 (optional) and Week 52 (optional) will be summarized in table with standard descriptive statistics for continuous variables and 95% CI for the mean.

Additionally, the absolute change of HRCT fibrosis score from baseline at Week 26 (optional) and Week 52 (optional) will be summarized in table with standard descriptive statistics for continuous variables and 95% CI for the mean.

The paired t-test will be performed to evaluate the changes in the variable from the baseline to Week 26 (optional) and Week 52 (optional), respectively. The type I error rate will be set to 5%.

Lung opacity (ground-glass attenuation)

The sign 'lung opacity' will be qualified separately using methodology described above for other signs, and its change over time will be assessed outside the framework of a total summed index of fibrosis (HRCT fibrosis score). Lung opacity should be graded as reticular abnormality to calculate the score for each zone, i.e. the percentage (%) area of opacity in a zone should be multiplied by the score of 2.

The percentage area of opacity at Baseline, at Week 26 (optional) and Week 52 (optional) will be summarized in table with standard descriptive statistics for continuous variables and 95% CI for *the* mean.

Additionally, the absolute change of percentage area of opacity from Baseline at Week 26 (optional) and Week 52 (optional) will be summarized in table with standard descriptive statistics for continuous variables and 95% CI for *the* mean.

Exacerbations

Pirfenidone—F. Hoffmann-La Roche Ltd

An exacerbation will be defined as an AE with special criteria, *i.e. only in case the exacerbation has led to death of a patient* (see [Section 5.2.1](#)). Rate of exacerbation will be reported in three following tables:

- Exacerbation cases during treatment period (until Week 26).

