Assessment of UIP signs

Assessment of UIP signs on HRCT will be performed using a semiquantitative method (see [Table 1-3](#)). Each lung will be divided vertically into three zones: upper zone, middle zone and lower zone. Margins between the zones on axial section are level of tracheal bifurcation and level of the right lower pulmonary vein. The upper lung zone is defined as the area of the lung above the level of the tracheal bifurcation, the lower lung zone is defined as the area of the lung below the level of the lower pulmonary vein and the middle lung zone is defined as the area of the lung between the upper and lower zones.

The HRCT findings will be graded on a scale of 1-4 based on the classification system: 1) normal attenuation; 2) reticular abnormality; 3) traction bronchiectasis; and 4) honeycombing. The presence of each of the above four HRCT findings should be assessed independently in three (upper, middle and lower) zones of each lung. The extent of each HRCT finding will be determined by visual estimation of the percentage (%) (to the nearest 5%) of parenchymal involvement in each zone, from 0 to 100. A total sum of all abnormalities in one zone of a lung cannot exceed 400%.

The score for each zone will be calculated by multiplying the percentage of the area by the mentioned above grading scale score (1-4). The zone scores for six zones of two lungs will be averaged to determine the total score for each patient. The overall HRCT score should be obtained by adding the averages for each index. The highest possible score is 400 points and the lowest score is 100 points using this calculation method.

The total score will be named as the “HRCT fibrosis score”. Semiquantitative assessment with HRCT fibrosis score calculation will be performed at initiation of treatment and 6 months later. For patients continuing therapy in real clinical practice after study completion additional assessment will be performed in a year of therapy.

Pirfenidone—F. Hoffmann-La Roche Ltd

Appendix 2

HRCT Protocol (cont.)

Table 1-3. Assessment of HRCT UIP signs in lungs.

Sign	Reticular abnormality	Honeycombing	Traction bronchiectases	Normal attenuation	Lung opacity
Upper zone RL ¹					
Middle zone RL					
Lower zone RL					
Upper zone LL ²					
Middle zone LL					
Lower zone LL					

¹ RL – right lung.

² LL – left lung.

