8.3. Exploratory Efficacy Analyses

eCRF form: “HRCT SCAN”, “ADVERSE EVENTS”.

HRCT fibrosis score

The HRCT findings will be evaluated using HRCT scoring system. One ILD radiologist will make assessments of 4 main findings in three zones of each lung. The six zone scores will be averaged to determine the total score for each patient. Score will be recorded at the initial diagnosis and after six and 12 months in a similar manner for further comparison. The mean \pm SD of HRCT fibrosis score like continuous variable will be determined obligatory at baseline, 6 months and optional at 12 months.

The values of HRCT fibrosis score at baseline, at Week 26 and Week 52 (optional) will be summarized in table with standard descriptive statistics for continuous variables and 95% CI for the mean.

Additionally, the absolute change of HRCT fibrosis score from baseline at Week 26 and Week 52 (optional) will be summarized in table with standard descriptive statistics for continuous variables and 95% CI for the mean.

The paired t-test will be performed to evaluate the changes in the variable from the baseline to Week 26 and Week 52 (optional), respectively. The type I error rate will be set to 5%.

Lung opacity (ground-glass attenuation)

The sign ‘lung opacity’ will be qualified separately using methodology described above for other signs, and its change over time will be assessed outside the framework of a total summed index of fibrosis (HRCT fibrosis score). Lung opacity should be graded as reticular abnormality to calculate the score for each zone, i.e. the percentage (%) area of opacity in a zone should be multiplied by the score of 2.

The lung opacity score at Baseline, at Week 26 and Week 52 (optional) will be summarized using standard descriptive statistics for continuous variables and 95% CI for the mean.

Additionally, the absolute change of lung opacity score from Baseline at Week 26 and Week 52 (optional) will be summarized in table with standard descriptive statistics for continuous variables and 95% CI for the mean.

**ML39355_STATISTICAL ANALYSIS PLAN_Final 2.0_17 June 2020**Exacerbations

An exacerbation will be defined as an AE with special criteria “Is this an exacerbation of IPF?” = “Yes”, i.e. only in case the exacerbation has led to death of a patient. Rate of exacerbation will be reported in three following tables:

- Exacerbation cases during treatment period (until Week 26).

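### The HRCT fibrosis score is read by eye at each time point with no provision to mask the reader to scan date or to randomise reading order, and it carries the only hypothesis test in an uncontrolled trial

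*Protocol*

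**What the plan says.** **Who reads.** Protocol Section 4.5.6.1: "Further semiquantitative assessments of CT scans for fibrosis scores will be performed by one central reader". SAP Section 8.3 agrees: "One ILD radiologist will make assessments of 4 main findings in three zones of each lung". The second central radiologist in Protocol Sections 3.1 and 4.5.6.1 is used for eligibility only.

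**How.** Under Appendix 2 of the protocol the reader estimates by eye, to the nearest 5%, how much of each of six lung zones shows each finding. The percentages are weighted 1 (normal), 2 (reticular), 3 (traction bronchiectasis) or 4 (honeycombing), and the zone scores are averaged. "The highest possible score is 400 points and the lowest score is 100 points using this calculation method".

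**When.** Section 4.5.6.1: "Semiquantitative analysis of CT scans with HRCT fibrosis score calculation should be performed in each timepoint". Appendix 2: "Semiquantitative assessment with HRCT fibrosis score calculation will be performed at initiation of treatment and 6 months later", with a further assessment at one year for patients who continue treatment. Section 6.4.3: "Score will be recorded at the initial diagnosis and after six and 12 months in a similar manner for further comparison".

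**How it is analysed.** SAP Section 8.3: "The paired t-test will be performed to evaluate the changes in the variable from the baseline to Week 26", and likewise to Week 52 where available, at a 5% type I error rate. SAP Table 2.15 reports both p-values, and SAP Section 6.6 plans no multiplicity adjustment. FVC, 6MWT, EQ-5D-5L and lung opacity are summarised descriptively, with confidence intervals for all but EQ-5D-5L.

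**What is not there.** Neither document says that dates or visit labels are hidden from the reader, or in what order a patient's scans are read. Appendix 2, the detailed HRCT protocol, is silent on both.

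**The concern.** A visual estimate can shift with the reader's experience over the months of a trial, or with an expectation of what a later scan should show. In a randomised trial much of such a shift would fall on both arms and cancel in the comparison. Here there is one arm and every patient is treated, so a shift tied to visit is added to the mean change from baseline. A paired t-test then asks only whether the change is consistent across patients. It cannot tell a consistent reading shift from a consistent change in the lung.

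At stake is the meaning of the two p-values in SAP Table 2.15. Appendix 2 says that HRCT serves response assessment in this study, so those p-values are likely to be read as evidence about response.

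**Working it through.** **1. The plan's own figure.** No sample size or power is stated for the HRCT test. The trial size comes from the precision of an FVC proportion (Protocol Section 6.1; SAP Section 5):

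n = p × q × (z/E)² = 0.601 × 0.399 × (1.96/0.125)² = 58.96, taken as 60.

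This reproduces. I use n = 60 below, and n = 40 to allow for missing scans.

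**2. What one reading step does to the score.** Zone score = sum of (percentage of area × weight); total = mean of six zones (Appendix 2). Moving 5% of the area between adjacent grades changes that zone by 5 × 1 = 5 points.

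- In one zone only: 5/6 = 0.83 points on the total.
- In all six zones: (6 × 5)/6 = 5 points on the total.

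**3. Effect of a drift on the paired t-test.** Let d be the systematic reading shift between two visits divided by the SD of the paired change. With no true change, the test statistic follows a noncentral t distribution with n − 1 degrees of freedom and noncentrality d√n. For d = 0.2 and n = 60 this is 0.2 × 7.746 = 1.55. The SAP does not say whether the test is one- or two-sided; two-sided 5% is assumed. The chance of p < 0.05 is then:

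| Drift d (in SD of change) | n = 60 | n = 40 |
|---|---|---|
| 0 | 5% | 5% |
| 0.1 | 12% | 9% |
| 0.2 | 33% | 24% |
| 0.3 | 63% | 46% |
| 0.5 | 97% | 87% |

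**4. The same in score points, n = 60.** The documents give no SD of change, so a range is assumed:

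| Assumed SD of change | 0.83-point shift | 5-point shift |
|---|---|---|
| 10 | 10% | 97% |
| 15 | 7% | 72% |
| 20 | 6% | 48% |
| 30 | 5% | 25% |
| 40 | 5% | 16% |

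A one-step shift confined to one zone hardly matters. The same step in every zone matters a good deal unless the SD of change is large.

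**5. After the fix.** If masked reading in random order removes any shift tied to visit, d = 0 and the rate returns to 5%. Ordinary reading error remains, but it adds to the SD and not to the mean change.

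**6. Whether anything needs the scores earlier.** Eligibility rests on the UIP pattern (Protocol Section 4.5.6.2, Table 2). The management rules in Table 3 of Section 5.1.2 do not use the fibrosis score. No interim analysis is planned (SAP Section 6.4), and one final report follows database lock (SAP Section 13). Nothing in the plan depends on reading the scans visit by visit.

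**The case against.** **The documents do not say that the reader knows the dates.** A reader of the plan might infer that scans are scored as they arrive by someone who knows each time point. The text does not establish that. The sentences on timing can be taken to say which scans are scored, not when the reader sits down or what labels are visible. The SAP's statement that blinding does not apply (Section 4.2) is based on Protocol Section 4.2, which concerns treatment assignment, so it does not show that the reader is unmasked either. A reading manual may exist: HRCT data pass through a vendor's database, and Section 9.4, cited for information on central reviewers, is not in the public text. This stands. What can be said is that the protocol and SAP do not provide for masking or reading order.

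**The endpoint is exploratory.** No success criterion depends on it. Being the only endpoint with a p-value does not make it the main evidence, since the 95% confidence interval for FVC change carries the same information as a test against zero. This also stands and limits the consequence.

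**A large shift is easy to construct but hard to defend.** Moving 5% of area from honeycombing to reticular in every zone gives 5 × (4 − 2) = 10 points. With n = 60, the expected t then exceeds 2 whenever the SD is below 10√60/2 = 38.7. A reader might conclude that the test would declare such a shift significant. But Table 2 admits patients with possible UIP, whom Appendix 2 describes as lacking honeycombing, so the shift cannot apply to everyone. At an SD of 38.7 the expected t is only about 2, so significance would follow only about half the time.

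**One reader is a strength.** A single reader and fixed acquisition settings limit other sources of variation. Agreed; the fix keeps both.

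**Masking would not allow attribution to the drug.** True in any uncontrolled study. It would still remove one avoidable, non-biological explanation of a change.

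**Conclusion.** The point holds as a gap in how the exploratory HRCT endpoint is read. A subjective score from one reader, called for at each time point in a single open-label arm, is taken to a paired t-test with no stated protection against a reading shift between visits. A drift of 0.2 SD of the paired change would raise the false-positive rate from 5% to about 33% with 60 patients.

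These rates show sensitivity and do not estimate the bias. They rest on an assumed drift, an assumed SD of change, a two-sided test, no true change, and complete scans in 60 patients (or 40). The direction is open: a reader might expect benefit from treatment or progression of disease. The primary FVC analysis is untouched. This is an inexpensive improvement worth making, not a flaw that threatens the trial's main result.

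**What to change.** In Protocol Section 4.5.6.1, Appendix 2 and SAP Section 8.3, state that dates and visit labels are removed from the images and that the same central reader scores each patient's baseline, Week 26 and any Week 52 scans in random order, in one batch, after that patient's last scan. If a reading manual already requires this, cite it in those sections.

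The cost is the de-identification work and later availability of the scores. No extra reader, scan or patient is needed, and the images are already digital and sent electronically to the central readers. Reading one patient's scans together also limits drift in the reader's standards over the course of the trial.

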4.5.6.2 Surgical Lung Biopsy

Histopathological assessment of the lung tissue samples obtained within 4 years before the Screening should be performed centrally for eligibility confirmation. Histopathological evaluation, if not available, is not repeated at the Screening.

Transbroncheal biopsy or BAL are not mandatory and will only be reviewed at the Screening, if available, to exclude other causes of PF.

Histopathologic criteria for UIP are outlined in [Appendix 3](#). Samples will be submitted and reviewed by one of the two central readers who are pathologists with expertise in IPF. Data regarding the pathology findings will be entered directly into the electronic case report form (eCRF).

The observations of the central readers in radiology and pathology will be stored in the clinical database. Based on the algorithm detailed in [Table 2](#), patient eligibility will be communicated to the study site by the Sponsor's designated vendor.

Table 2 Summary of Select Criteria for Diagnosis of IPF

	Surgical Lung Biopsy Not Available	Pathology Panel: Definite UIP	Pathology Panel: Probable UIP	Pathology Panel: Possible UIP	Pathology Panel: Inconsistent with UIP or Not Classifiable
Radiology Panel: Definite UIP	Eligible	Eligible	Eligible	Eligible	NOT Eligible
Radiology Panel: Possible UIP	Eligible	Eligible	Eligible	NOT Eligible	NOT Eligible
Radiology Panel: Inconsistent with IPF	NOT Eligible	NOT Eligible	NOT Eligible	NOT Eligible	NOT Eligible

4.5.7 Spirometry and DL_{CO} Measurements

Spirometry and PFT will be standardized and performed as described in ATS recommendations (ATS 2005).

FVC

FVC is the maximal volume of air exhaled with maximally forced effort from a maximal inspiration, i.e. vital capacity performed with a maximally forced expiratory effort, expressed in litres at body temperature and ambient pressure saturated with water vapour (ATS 2005).

At screening, spirometry measurements of FVC will be performed before and after administration of albuterol (or salbutamol) from a metered dose inhaler. Four separate doses of 100 mg should be used when given by metered dose inhaler using a spacer. Tests should be repeated after a 15-min delay. During further visits, bronchodilator test is not necessary to perform.

DL_{CO}

DL_{CO} will be measured by determining the diffusing capacity of the lung for carbon monoxide corrected to hemoglobin. DL_{CO} measurement should be performed before or at least 30 min after the last bronchodilator puff, *in case bronchodilator test has been*

Pirfenidone—F. Hoffmann-La Roche Ltd

performed. It is measured by a single breath technique where helium and carbon monoxide are rapidly inspired, held for several seconds and then expired with the measurement of the remaining carbon monoxide. Comparison of the inspired and expired CO fractions allows calculation of DL_{CO} (Ranu et al. 2011).

Results of DL_{CO} measurements should be corrected to patients' hemoglobin (Hb) using one of the formulas (Cotes et al. 1979):

$$\text{Hb-corrected DL}_{\text{CO}} \text{ for men: } \text{DL}_{\text{CO}} \times (10.22 + \text{Hb}) / (1.7 \times \text{Hb})$$

$$\text{Hb-corrected DL}_{\text{CO}} \text{ for women: } \text{DL}_{\text{CO}} \times (9.38 + \text{Hb}) / (1.7 \times \text{Hb})$$

where Hb indicates the value of hemoglobin, in g/dL. If the Hb value is reported in g/L, then the Hb value is divided by 10. If the Hb value is reported in mmol/L, then the Hb value is divided by 0.6206.

Use the hemoglobin value available on the same day if possible; otherwise, the closest hemoglobin value before or after the actual DL_{CO} assessment date should be used. If the two values are equidistant, the value before the actual DL_{CO} assessment should be used (Cotes et al. 1979).

Lung function assessments in one patient during the study should be performed using the same equipment and by the same investigator. All spirometry and DL_{CO} data collected throughout the study will be evaluated by local readers. Data for FVC and DL_{CO} will be entered by the study staff into the eCRF electronically.

4.5.8 Laboratory, Biomarker, and Other Biological Samples

All samples for laboratory tests (hematology, blood chemistry, serologic tests) will be analyzed in the study site's local laboratory.

Blood samples should be obtained in fasted patients and handled appropriately. The following parameters will be utilized in the study:

- hematology (plasma): white blood cells (WBC) count, red blood cells (RBC) count, hemoglobin, hematocrit, platelet count, (relative) differential WBC count (neutrophils, eosinophils, basophils, monocytes, lymphocytes);
- blood chemistry panel (serum or plasma): albumin, alkaline phosphatase (AP), ALT, AST, direct bilirubin, total bilirubin, total protein, albumin, cholesterol, creatine kinase (CK), creatinine, triglycerides, gamma-glutamyl transferase

Pirfenidone—F. Hoffmann-La Roche Ltd

(GGT), glucose, lactic dehydrogenase (LDH), calcium, phosphorus, magnesium, potassium, sodium, urea nitrogen, uric acid;

- serologic tests (at screening only, exclusion tests): rheumatoid factor, anticyclic citrullinated peptide and antinuclear antibody titer.

Creatinine clearance

Creatinine clearance should be assessed at the Screening for eligibility confirmation using the following formula by Cockcroft-Gault (Cockcroft DW et al, 1976):

For serum creatinine concentration in mg/dL:

$$\text{CrCl (mL/min)} = (140 - \text{age (years)}) \times \text{weight (kg)} \times 1.0 / 72 \times \text{serum creatinine (mg/dL)}$$

For serum creatinine concentration in $\mu\text{mol/L}$:

$$\text{CrCl (mL/min)} = (140 - \text{age (years)}) \times \text{weight (kg)} \times 1.0 / 0.81 \times \text{serum creatinine (\mu mol/L)}$$

Pregnancy test

All women of childbearing potential will have a urine pregnancy test at the Screening and on Day 1 before start of treatment. Only women with negative pregnancy test will be included in the study. Urine pregnancy tests will be performed repeatedly at specified subsequent visits as scheduled in the [Appendix 1](#).

If a urine pregnancy test is positive, it must be confirmed by a serum pregnancy test. Women with confirmed positive pregnancy test should be immediately withdrawn from the study treatment (see [Section 5.4.3](#)). Urine pregnancy test will be performed by the investigator using test-strips with least sensitivity to human chorionic gonadotropin (hCG) of 10 mLU/mL.

The investigator can perform clinical laboratory assessments more frequently, if it is clinically indicated.

For sampling procedures, storage conditions, and shipment instructions, see the laboratory manual. Biological samples will be destroyed immediately after analyzing.

When a patient withdraws from the study, samples collected prior to the date of withdrawal may still be analyzed, unless the patient specifically requests that the samples be destroyed or local laws require destruction of the samples.

Pirfenidone—F. Hoffmann-La Roche Ltd

Data arising from sample analysis will be subject to the confidentiality standards described in [Section 8.4](#).

